This outcome will be measured from transplant operation start time ("knife to skin") till discharge from hospital, measured in days and will be estimated using competing risks analysis. Discharge from hospital will be considered as the event and death prior to discharge will be considered as the competing risk. Median (IQR) hospital stay from the cumulative incidence curve will be reported for each trial arm and overall. Although if there are no deaths, the Kaplan-Meier method will be used. To accommodate a random centre effect and adjustment for participant weight and donor type, Cox regression analysis with a frailty term will be used to compare time to discharge between treatment arms. Participants who have not been discharged will be censored at the point of last contact. Participants who die will be censored. The estimate of the hazard of discharge from this model should be interpreted with caution because it does not properly account for the competing risk of death. However, since the number of deaths is predicted to be small, the impact of the competing risk is likely to be negligible. This will be explored by examining the cumulative incidence function for death.

Transplant kidney function at 1, 3, 7 and 90 days

This will be calculated using the creatinine-based univariate Schwartz formula (4) to determine eGFR:

eGFR = 36.5 x (height/ plasma creatinine concentration)

where height is measured in cm and plasma creatinine in micromol/L (1mg/dl = 0.01131222 micromol/L). For day 1 and 3, this data will be obtained from the blood data measurements taken routinely. If multiple measurements are recorded on the same day, then we will use the last measurement taken for each day, as this is likely to be the lowest and gives most time for creatinine to be in steady state. For day 7 and 90 a single measurement is being collected via the MACRO database and UK Transplant Registry respectively. For day 1, 3 and 7, the participant height recorded at transplant will be used. For 90 days, the participant's height at this timepoint will be used, which will be obtained from the UKTR. The mean and standard deviation of eGFR at each timepoint will be presented by trial arm and overall.

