A repeated measures mixed Normal linear regression will be used to assess whether kidney function over days 1,3 and 7 are different between the two treatment arms, adjusting for donor type (living vs deceased donor), participant weight pre transplant (<20kg vs ≥20kg pre-transplant) and day of measurement. In addition, two random

Statistical Analysis Plan

effects will be included in the model to account for individual participant effects and transplant centre. Residual plots from the normal linear regression will be examined. If there is any evidence of skew or non-constant variance, repeated measures mixed normal linear regression of log-transformed eGFR will be used to assess whether mean log- eGFR are different between the two treatment arms, adjusting for donor type (living vs deceased donor), participant weight pre transplant (<20kg vs ≥20kg pre-transplant) and participant and transplant centre as random effects.

A separate mixed Normal linear regression will be used to assess whether mean eGFR is different between the two treatment arms at day 90, adjusting for donor type (living vs deceased donor), participant weight pre transplant (<20kg vs ≥20kg pre-transplant) and transplant centre as a random effect. Residual plots from the normal linear regression will be examined. If there is any evidence of skew or non-constant variance, mixed normal linear regression of log-transformed eGFR at 90 days will be used to assess whether mean log-eGFR are different between the two treatment arms, adjusting for adjusting for donor type (living vs deceased donor), participant weight pre transplant (<20kg vs ≥20kg pre-transplant) and transplant centre as a random effect.

Other electrolyte abnormalities within the first 72 hours post transplantation This includes the following:

- Hypernatraemia (defined as plasma sodium concentration > 145mmol/l)
- Hyperkalaemia (defined as plasma potassium concentration > 5.5mmol/L)
- Hypokalaemia (defined as plasma potassium concentration < 3.5mmol/L)
- Non anion-gap acidosis (defined as plasma bicarbonate < 20mmol/L and anion gap < 20mmol/L. Anion gap will be calculated as the sum of plasma sodium and plasma potassium, minus the sum of plasma chloride and plasma bicarbonate).
 Where possible, these components should be obtained simultaneously, but where this is not possible, samples should be collected within an hour.
- Hyperglycaemia (defined as random blood glucose > 5.5 mmol/L)

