https://www.who.int/toolkits/growth-reference-data-for-5to19-years will be used to determine the height percentiles. Heights in cm will be converted to inches by dividing by 2.54 and will utilise the height at transplant. The mean minimum and maximum normalised systolic blood pressure, with standard deviation, will be presented separately for each trial arm and overall, for each day. A repeated measures mixed Normal linear regression will be used to assess whether mean percentiles over the three days are different between the two treatment arms, adjusting for donor type (living vs deceased donor), participant weight pre transplant (<20kg vs ≥20kg pre-transplant) and day of measurement. In addition, two random effects will be included in the model to account for individual participant effects and transplant centre. Residual plots from the normal linear regression will be examined. If there is any evidence of skew or non-constant variance, repeated measures mixed normal linear regression of log-transformed percentile will be used to assess whether mean log-percentile are different between the two treatment arms, adjusting for donor type (living vs deceased donor), participant weight pre transplant (<20kg vs ≥20kg pre-transplant) and participant and transplant centre as random effects.

Number of changes in intravenous fluid composition within the first 72 hours post-transplant

A change to intravenous fluid composition will be defined as any modification to the composition of the fluid administered to the participant. The number of changes in fluid will be counted as follows:

- If the participant is initially given something different to which they were randomised, this will be counted as the first change
- Subsequent changes will be counted based on the fluid being administered before the change.
- Diluent used for drug infusions, will not be counted.

For example:

- if the participant was randomised to standard arm, was first administered Hartmann's solution, then 0.9% sodium chloride, and then Hartmann's solution again, this would be counted as two changes.
- If the participant was randomised to Plasma-Lyte, was first administered 5% glucose, then received Plasma-Lyte 148 and then Plasma-Lyte® 148 & Glucose 5%, this would count as three changes.

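### Early kidney function is defined at days 1, 3 and 7, but the only modelled comparison is one three-day average, so no early day gets an adjusted difference, interval or test

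*SAP*

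**What the plan says.** **Outcome.** SAP section 3.4 defines the secondary outcome as "Transplant kidney function at 1, 3, 7 and 90 days".

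**Description.** The same section promises daily summaries: "The mean and standard deviation of eGFR at each timepoint will be presented by trial arm and overall".

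**Model for the early days.** One repeated-measures Normal model addresses "whether kidney function over days 1,3 and 7 are different between the two treatment arms". Its fixed effects besides treatment are donor type, "participant weight pre transplant (<20kg vs ≥20kg pre-transplant) and day of measurement". Two random "effects will be included in the model to account for individual participant effects and transplant centre". No treatment-by-day term is specified. Day 90 has its own separate model.

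**Test.** Section 3.2 takes the p-value from models fitted with and without the treatment term.

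**Table.** The kidney function table in section 4.4 has a row of unadjusted mean and SD for each of days 1, 3 and 7, then one adjusted mean difference with one interval and one p-value for the three days together.

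**Log-scale fallback.** If residuals are skewed or their variance is not constant, eGFR is log-transformed. The adjustment list for that model is donor type, weight group and "participant and transplant centre as random effects". Day is not in it.

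**Systolic pressure.** The model has the same form over days 1 to 3. Its stated question is "whether mean percentiles over the three days are different between the two treatment arms", and its log-scale fallback also leaves out day.

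**The concern.** The outcome is worded by day and the analysis by average. A model with a treatment main effect and no interaction assumes the same between-arm difference on days 1, 3 and 7, a period over which a new graft's function is changing. If the true difference varies over the week, the single coefficient is a mixture: a late difference is diluted, and differences of opposite sign cancel.

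What is at stake is how a secondary result is read. A null average could be reported as no effect on early kidney function when the model was not set up to estimate a difference at day 7. A reader who sees a gap in the daily means would have no adjusted estimate or interval with which to judge it, and any day-by-day comparison made later would be post hoc.

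**Working it through.** The SAP gives no power, SD or correlation for eGFR, so there is no planned figure to reproduce.

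**Inputs from the SAP**
- Days 1, 3 and 7; treatment and day as main effects; random participant and centre effects (section 3.4).
- Two-sided 5% level (section 3.2).
- 128 analysable children, 64 per arm (section 1.6). This sets the scale of the example only; the power comparison below does not depend on it.

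**Assumed.** Within-child correlation ρ from 0.3 to 0.7. SDs are either equal on the three days or rise in the ratio 0.4 : 0.7 : 1.

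**Step 1: what the coefficient estimates.** With complete data and a random participant intercept, treatment is balanced over days, so the coefficient is the plain mean of the daily differences, (d1 + d3 + d7)/3, whatever ρ is.

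| True differences (days 1, 3, 7) | Modelled difference |
|---|---|
| 0, 0, D | D/3 |
| 0, D/2, D | D/2 |
| -D, 0, D | 0 |
| D, D, D | D |

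On the log scale, a day-7-only ratio of 1.30 becomes 1.30^(1/3) = 1.09.

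If a fraction m of day-7 values is missing, the day-7 share falls a little. At ρ = 0 it is (1 - m)/(3 - m), which is 0.9/2.9 = 0.31 for m = 0.1 and 0.8/2.8 = 0.29 for m = 0.2. At ρ = 0.8 the generalised least squares expectation is 0.30 and 0.27.

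**Step 2: power for a day-7-only difference, equal SDs.** For one day, SE = SD × √(2/64). For the average, SE = SD × √((1 + 2ρ)/3) × √(2/64). The ratio of the average's noncentrality to that of day 7 alone is therefore (1/3)/√((1 + 2ρ)/3). If day 7 alone has 80% power, its noncentrality is 1.960 + 0.842 = 2.802, so D = 2.802 × √(2/64) = 0.495 SD.

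| ρ | Ratio | Noncentrality of average | Power of average |
|---|---|---|---|
| 0.3 | 0.456 | 1.279 | 25% |
| 0.5 | 0.408 | 1.144 | 21% |
| 0.7 | 0.373 | 1.044 | 18% |

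**Step 3: other patterns, same 80% reference**
- Day 7 only, SDs 0.4 : 0.7 : 1. The ratio is 1/√(1.65 + 2.76ρ), which is 0.635 at ρ = 0.3 and 0.528 at ρ = 0.7. Power is 43% and 32%.
- Build-up 0, D/2, D. The ratios are 1.5 times those for day 7 only. Power is 48% to 35% with equal SDs and 76% to 60% with rising SDs (ρ = 0.3 to 0.7).
- Constant D, equal SDs. The ratio is 1/√((1 + 2ρ)/3), which is 1.369, 1.225 and 1.118 at ρ = 0.3, 0.5 and 0.7. Power is 97%, 93% and 88%.

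**Step 4: width of daily intervals.** With equal SDs, a single-day interval is √(3/(1 + 2ρ)) times as wide as that of the average: 1.37, 1.22 and 1.12 at ρ = 0.3, 0.5 and 0.7.

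**The case against.** The strongest reply is that the average is the intended target. The analysis sentence asks about function over the three days, a main-effect model answers that question, and pooling correlated early measurements is a common choice that is more powerful when the effect is steady (Step 3). This stands in part: an average is legitimate if declared. But the outcome is still named at each day, and nowhere does the SAP say that the three-day average is what it means by that.

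Four stronger readings are tempting and should not be drawn.

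- **That daily results disappear.** They do not. Means and SDs by arm are tabulated for each day, so a day-7 gap would be visible at full size. What is missing is its adjusted estimate, interval and test. Day 90 is not averaged with the early days.
- **That the SAP itself concedes the effect must grow from day 1 to day 7.** The phrase "as this is likely to be the lowest and gives most time for creatinine to be in steady state" explains only why the last sample within a day is used. The documents do not say how a treatment effect would evolve. Trial fluid is scheduled up to day 3 (section 2.1), so an early effect that fades is also possible.
- **That the model fixes equal variances and correlations.** A random participant intercept alone would imply this, but the SAP does not state the residual covariance, and it provides for residual checks with a log-scale fallback.
- **That systolic pressure has the same defect.** That outcome is not named at particular days, its stated question is the three-day mean, and it has no day 7.

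It is also fair to say that more secondary estimates have a cost in a trial powered only for its primary outcome and with no multiplicity adjustment.

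**Conclusion.** The point holds for early eGFR as a mismatch between the outcome as named and the comparison as modelled. No adjusted difference, interval or test is planned for day 1, 3 or 7. With complete data, a day-7-only difference is estimated at one third of its size; that result needs no assumption about SDs or correlations.

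The power consequence does depend on assumptions. Against an 80% reference for day 7 alone, the averaged test has 18-25% (day-7-only effect, equal SDs), 32-43% (day-7-only, rising SDs), 35-76% (build-up across both SD patterns) or 88-97% (constant effect, equal SDs). A reader might infer that the planned model generally loses power; it does so only when the effect is uneven across days.

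The omission of day from both log-scale fallbacks is a separate drafting gap. Without day in the model, the change in mean level between days is left in the residual, and if the arms differ in which days are recorded it can leak into the treatment estimate.

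These are secondary outcomes and the primary result is unaffected. The change is worth making because it is cheap and lets the trial answer its outcome as named.

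**What to change.** **eGFR model.** Fit day as a factor with a treatment-by-day term. Use a within-child covariance that lets variances differ by day, for example unstructured over the three days in place of the participant intercept, and keep centre random. Report the adjusted difference and 95% interval at days 1, 3 and 7, and keep the three-day average as a summary line. State that p-values come from these contrasts, because dropping every treatment term at once would give a joint three-degree-of-freedom test rather than a test of the average or of any one day.

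**eGFR log-scale fallback.** Make the same change and include day. Report ratios at each day and on average.

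**Systolic pressure.** Add day to the log-scale fallback. Day-specific estimates are optional.

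**Table.** Add three adjusted rows to the kidney function table in section 4.4.

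**Cost.** SAP wording and three more secondary estimates, without multiplicity adjustment and with intervals about 12-37% wider than that of the average (equal SDs, ρ = 0.7 to 0.3). No new data are needed. If the sponsor prefers the average alone, the minimum is to say so in the outcome definition, accepting that the trial then makes no inference about any single early day.

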- Hypomagnesaemia (defined as plasma magnesium concentration < 0.7 mmol/L)
- Hyperchloraemia (defined as plasma chloride concentration > 107mmol/L)
- Excessive rate of reduction in plasma sodium concentration (defined as >1mmol/L/hour averaged over 6 hours)
- Excessive magnitude of reduction in plasma sodium concentration (defined as > 10mmol/L from pre-transplant level)

The number and percentage of participants who experience each of these events will be presented by trial arm and overall, alongside the median and interquartile range of the number of each event experienced. To test for differences in the proportion of participants experiencing each event, separate mixed logistic regression models will be used. These will be adjusted for donor type (living vs deceased donor), participant weight (<20kg vs ≥20kg pre-transplant) and transplant centre as a random effect. The adjusted odds ratio for treatment, with 95% confidence interval, will be presented from this model, with the p-value from the likelihood ratio test when including and excluding the treatment term from the model.

Maximum and minimum systolic blood pressure

The minimum and maximum systolic blood pressure will be taken for each day, for the first 3 days post-transplant (the measurement recorded in the database will have been sustained on 3 repeated values on each day). The values will be normalised to age and height percentile by the statistician, using the process as specified in https://www.nhlbi.nih.gov/files/docs/resources/heart/hbp ped.pdf and

Statistical Analysis Plan

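### The log-scale fallback models for repeated eGFR and blood pressure percentile drop day of measurement, which the models they replace include

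*SAP*

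**What the plan says.** In SAP section 3.4, the model for kidney function over days 1, 3 and 7 adjusts for donor type, "participant weight pre transplant (<20kg vs ≥20kg pre-transplant) and day of measurement", with random effects for participant and transplant centre. The fallback follows in the same paragraph: on any sign of skew or unequal variance in the residual plots, "repeated measures mixed normal linear regression of log-transformed eGFR will be used". Its adjustment list is written out again as donor type, "participant weight pre transplant (<20kg vs ≥20kg pre-transplant) and participant and transplant centre as random effects". Day is not in it.

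The systolic blood pressure outcome, measured "for the first 3 days post-transplant", has the same pattern. The main model includes day. The fallback, "repeated measures mixed normal linear regression of log-transformed percentile will be used", lists donor type, weight and the two random effects only.

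Nothing elsewhere settles the matter. The general adjustment rule in section 3.2 names site, weight and donor type. The footnotes to the eGFR and blood pressure tables in section 4.4 name the same three, even though the main models also contain day.

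**The concern.** A switch to the log scale should change the scale of the outcome and nothing else. Here it also removes a covariate that explains systematic change within each child. eGFR can be expected to move during the first week after a transplant, so without day that movement goes into the residual. It then competes with the participant variance component. If the mix of observed days differs between arms, it also leaks into the treatment contrast.

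The fallback may well be the model that is used. Its trigger is any evidence of skew or non-constant variance, which is a low bar, and eGFR is a positive ratio of height to creatinine. A programmer following the text literally would fit a poorer model than the one it replaces. A programmer who restored day would be departing from the written plan after seeing the data.

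**Working it through.** **Text.** The single-measurement outcomes with a log fallback (weight gain, day-90 eGFR, duration of hyponatraemia, sodium variation, maximum rate of sodium change) all repeat their main adjustment list unchanged. Only the two repeated-measures outcomes lose a term, and it is the same term in both.

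**Inputs.** The SAP gives no SDs, no day trend and no day-7 missingness by arm, so everything numerical below is assumed. Take 64 children per arm (the 128 in section 1.6 before drop-out), three visits, between-child SD τ and within-child SD σ on the log scale, and no covariates other than treatment.

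**Standard error, complete data.** Let SS be the sum of squared deviations of the three log day medians from their mean.
- Between-child mean square: B = σ² + 3τ² (126 df).
- Within-child mean square without day: W = σ² + SS/2 (256 df).
- SE of the treatment effect = √(2B/192), with or without day, as long as W is below B.
- If W exceeds B, the participant variance is estimated at zero. B is then replaced by the pooled value P = (126B + 256W)/382.
- The condition W > B reduces to τ < √(SS/6), whatever σ is.

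| Assumed medians, days 1/3/7 | τ = σ | SS | B | W | P | SE with day | SE without | Threshold for τ |
|---|---|---|---|---|---|---|---|---|
| 25/50/70 | 0.25 | 0.551 | 0.250 | 0.338 | 0.309 | 0.051 | 0.057 | √(0.551/6) = 0.30 |
| 20/50/80 | 0.20 | 0.994 | 0.160 | 0.537 | 0.413 | 0.041 | 0.066 | √(0.994/6) = 0.41 |

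In both rows τ was chosen below its threshold. In simulation, power falls from 82% to 76% for a 0.15 log effect in the first row, and from 84% to 43% for a 0.12 effect in the second. With τ = 0.45, above both thresholds, nothing changes.

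A separate simulation (1,500 null trials per scenario, random-intercept REML) agrees:
- Day effects 0/0.6/0.9, SDs 0.5 and 0.3: SE 0.093 with day and 0.093 without.
- Day effects 0/0.9/1.4, SDs 0.3 and 0.4 (threshold 0.41, so below it): without day the model SE is 0.078 against an empirical 0.066, and type I error is 1.7%.

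**Bias, day-7 eGFR missing unequally.** A child without day 7 contributes a mean over days 1 and 3 only. For day effects 0/0.6/0.9 that mean is 0.3, against 0.5 over all three days, a gap of −0.2. With 5% v 20% missing, the expected bias is roughly 0.15 × (−0.2) = −0.03 log units, against the arm with more missing. Children with fewer values get somewhat less weight, so the result can be a little smaller. Simulated results without day:

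| Day effects | Day 7 missing by arm | Bias (log) | Ratio | Type I error |
|---|---|---|---|---|
| 0/0.6/0.9 and 0/0.9/1.4 | 5% v 20% | −0.026 to −0.036 | 0.965 to 0.975 | 4.5% to 7.5% |
| same | 0% v 25% | −0.037 to −0.067 | 0.935 to 0.964 | 7.3% to 10.0% |
| same | 10% v 10% | at most 0.004 in size | 0.996 to 1.000 | 2.2% to 6.2% |
| 0/0.1/0.15 | any of the above | at most 0.011 in size | 0.989 to 1.001 | 3.5% to 6.3% |

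With day kept in, bias stayed within 0.005 in every scenario, and type I error lay between 3.7% and 6.5%, which is simulation noise around 5%.

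Both unequal scenarios average 12.5% missing overall, below the 25% at which section 3.8 withholds an outcome, so such results would be reported.

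**The case against.** The strongest reply is that this is a drafting slip with little practical effect. The fallback is still called a repeated-measures model and reads as the log version of the one before it. The table footnotes omit day even for the main model, so the SAP's adjustment lists are not always complete, and a trial statistician would probably keep day anyway. This lowers the chance of harm but does not cure the text. The fallback list is written out in full, and section 3.2 says that footnotes will state the variables adjusted for.

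On consequences the reply largely succeeds, and three stronger readings should be set aside.
- A reader might infer that the standard errors will be wrong in general, or that a fall in power such as 84% to 43% is to be expected. The documents give no SD or trend to support that. The effect needs a between-child SD below the thresholds above.
- A reader might infer an excess of false positives. With complete data the error goes the other way. An excess appears only with unequal missingness and a steep trend.
- A reader might carry the day-7 argument over to blood pressure. Blood pressure has no day-7 value. Bias there would need unequal missingness across days 1 to 3 as well as a day trend in the percentiles, and neither is shown.

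Nothing in the SAP predicts unequal day-7 missingness either. Section 3.8 expects missing data from death or withdrawal to be very rare. What can be said is that day 7 comes from a different source from days 1 and 3 ("For day 7 and 90 a single measurement is being collected via the MACRO database and UK Transplant Registry respectively") and that outcomes are not imputed, so the possibility is not excluded.

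**Conclusion.** The inconsistency is certain: both log-scale fallbacks omit a term that their main models contain, no reason is given, and nothing is gained by the omission. Its numerical effect is conditional.
- With complete data the estimate is unchanged. The standard error is unchanged too, unless the trend dominates between-child variation, and then the test is conservative.
- For eGFR, a steep trend with day 7 missing in 5% v 20% would bias the treatment ratio by about 3%, and by about 4% to 7% at 0% v 25%.
- For blood pressure no numerical consequence has been shown.

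All of these sizes rest on assumed trends, SDs and missingness rates, with centre, weight and donor type left out of the calculation. Only secondary outcomes are affected. The primary analysis and the separate day-90 eGFR model are not. The correction is worth making because it is cheap and removes a choice between two models after the data are seen, not because the trial's conclusions are at risk.

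**What to change.** In section 3.4, add day of measurement as a categorical fixed effect to the log-transformed eGFR model and to the log-transformed percentile model, so that each differs from its main model only in the scale of the outcome. In section 4.4, add day to the adjustment footnotes for the day 1, 3 and 7 eGFR comparison and for the blood pressure table. The day-90 eGFR comparison shares the eGFR table but has no day term, so its footnote should remain separate.

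The cost is a few words in two paragraphs and two footnotes. No extra data are needed, and neither the sample size nor the primary analysis changes.
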